STRIDE SAP

STRATEGIES TO REDUCE INJURIES AND DEVELOP CONFIDENCE IN ELDERS (STRIDE)

RANDOMIZED TRIAL OF A MULTIFACTORIAL FALL INJURY PREVENTION STRATEGY

STATISTICAL ANALYSIS PLAN

Version 2.0

November 25, 2019

The SAP was prepared by the blinded trial statisticians:

[name]

[name]

[name]

[name]

Revisions to the SAP were done before unblinding of the data.

STRIDE SAP

Modification to the SAP on 2-10-2020 for the Analysis of the Secondary Outcome All Falls

For the secondary outcome, all falls, the dates of events were not recorded. Thus, the analytic plan for first fall was modified from a time-to-event analysis to a practice-level Poisson model using time from baseline to the midpoint of the interview window in which the first fall was recorded as an offset in the model. [Note, the practice-level model was the default model when issues were encountered with patient-level models.] The lack of actual event times also precluded the calculation of cumulative incidence rates, which were replaced by event rates per person year of follow up. The analysis of recurrent falls was analyzed using the same method as the other recurrent event outcomes, i.e., a practice-level Poisson model with an offset for total follow-up time.

Modification to the SAP on 8-1-2020 for the Analysis of the Secondary Outcome All Falls

For the secondary outcome, all falls, the dates of events were not recorded and the exact counts of the number of events were also not recorded. Thus, a proper analysis of time to first fall and recurrent falls could not be done.

STRIDE SAP

TABLE OF CONTENTS

STUDY SUMMARY

PROTOCOL VERSION HISTORY

APPENDIX A. Prototype DSMB Tables and Figures

APPENDIX B. Interim Monitoring Plan

STRIDE SAP

STUDY SUMMARY (revised 7/31/2018)

Title	RANDOMIZED TRIAL OF A MULTIFACTORIAL FALL INJURY PREVENTION STRATEGY
Study Design	The design is a cluster randomized, parallel group superiority trial with practices stratified by healthcare system and patients nested within practices. The unit of randomization is the practice.
Study Duration	6 years
Trial Sites	10 trial sites: The Partners' Health Care System; Essentia; Hopkins Health Care System; HealthCare Partners; Reliant Health Care System; Mount Sinai Health Care System; University of Pittsburgh Health Care System; University of Texas Medical Branch Health Care System; University of Iowa Health Care System; University of Michigan Health Care System.
Objective	Conduct a cluster-randomized trial to determine the effectiveness of an evidence-based, patient-centered multifactorial fall injury prevention strategy.
Number of Subjects	The original target sample size was 6,000 participants enrolled from 86 practices to provide 90% power to detect a 20% reduction in the rate of the primary outcome with intervention relative to control. Later, the duration of the trial was extended to a total of 40 months (20 months of recruitment and an additional 20 months of follow-up), which reduced the target sample size to 5,322 participants. Recruitment ended after 20 months on March 31, 2017, with a total of 5,451 participants enrolled.
Main Inclusion Criteria	Community-living persons, 70 years or older, who are at increased risk for serious fall injuries.
Intervention	An evidence-based patient-centered intervention that combines elements of a multifactorial, risk factor-based, standardly-tailored fall prevention strategy developed at Yale, practice guidelines offered by the CDC's "STEADI" toolbox and the joint American Geriatrics Society/British Geriatrics Society guidelines, and ACOVE practice change approach.
Duration of Intervention	A minimum of 20 months and a maximum of 40 months.
Primary Outcome	The primary outcome is serious fall injuries, operationalized as a fall resulting in: (1) (fracture other than thoracic/lumbar vertebral; joint dislocation; or cut requiring closure) AND any medical attention; OR (2) (head injury; sprain or strain; bruising or swelling; or other) requiring hospitalization.
Primary Analysis	The risk of any serious fall injury (i.e., time to first event) will be analyzed using a survival model that incorporates competing risks (due to death) and clustering. In this analysis, participants who are lost to follow-up without a prior serious fall-related injury will be censored at their date last seen. In a secondary analysis, we will adjust for the pre-specified set of baseline covariates to examine their influence on the intervention effect.

STRIDE SAP

Secondary Outcomes	Number of falls, number of all fall injuries, and measures of well-being.
Adaptive Components	Adaptive components of the trial include: 1) monitoring the accrual rate to determine whether the study eligibility criteria need to be reconsidered if recruitment is lower than expected, taking into account that any changes could affect the inferences; 2) monitoring the potential for ascertainment bias because of interactions between the FCMs and study participants and changing the primary outcome definition if necessary; 3) monitoring the primary outcome rate to determine whether the outcome needs to be adapted, e.g., from time to first serious fall-related injury to time to all recurrent serious fall-related injuries if the former rate is too low, affecting the power of the study; 4) interim monitoring for efficacy or futility, if necessary; and 5) refining the analytic methods based on the validity of the assumptions; such an adaptation will be done blinded to treatment, e.g., if the death rate is low, competing risks could be considered as a secondary, rather than a primary, analysis.
Interim Analysis	Interim monitoring will focus on patient accrual, baseline comparability of treatment groups, protocol adherence, data completeness and quality, accrual of fall events, safety, and efficacy or futility.

STRIDE SAP

PROTOCOL VERSION HISTORY (revised 7/31/2018)

Version	Date	Changes
2.7	7/31/2018	1. Extend the study from a minimum of 20 and maximum of 40 months follow-up to a minimum of 24 and maximum of 44 months of follow-up. Final end date of the study, including the analytic phase is now extended to April 30, 2020.
2.6	6/1/2018	1. The definition of the primary outcome has been modified to reflect the recommendations of the Ad Hoc Expert Panel established by the NIA and NIA's concurrence with this recommendation.
2.5	12/13/2017	
 1. Duration of the study changed from 36 months (18 months of recruitment and a minimum 18 months of follow-up) to 40 months (20 months of recruitment and a minimum of 20 months of follow-up). 2. Target sample size adjusted to n=5,322 for a 40-month study instead of n=6000 for a 36-month study. 3. Interim monitoring was changed from efficacy and futility to efficacy or futility, if necessary.
2.4	6/27/2017	1. Clarification of the Adjudication process with CMS
2.3	1/28/2016	1. Changed the lower age limit for eligibility from 75 to as low as 70, if needed based on recruitment.
2.2	6/19/2015	
 1. Eliminate the postal questionnaire to ascertain fall/fall injury data. Instead, obtain these data through telephone calls from the RAC to all participants. (Note: all STRIDE participants will continue to use the fall calendars as a memory aid). 2. Change the timing of follow-up calls to patients to inquire about falls/fall injuries from every 3 months to every 4 months. 3. To comply with Pennsylvania state law, the list of people who are eligible to serve as proxy respondents for people who are unable to provide informed consent due to cognitive or hearing impairment has been adjusted.
2.1	3/25/2015	Original

STRIDE SAP

1. BACKGROUND

Approximately one in three older Americans falls each year and 20-30% of those who fall suffer moderate to severe injuries such as lacerations, hip fractures, or head trauma. The problem is important particularly among those 75 years and older when the incidence of falls rises dramatically. Among older adults, falls are the leading cause of both fatal and nonfatal injuries. In 2010, 2.3 million nonfatal fall injuries were treated in emergency departments and more than 662,000 of these patients were hospitalized. These numbers will rise with the aging of the baby boomers. In addition, many who do not sustain injuries develop fear of falling, which may result in self-limiting their activities, leading to reduced mobility and loss of physical fitness, further increasing their risk of falling.

Despite decades of research that has demonstrated conclusively that many falls in the elderly can be prevented, quality of care for falls remains low. Fewer than half of those who fall each year discuss their falls or fall prevention with a health care provider. Moreover, only a third of elderly patients in primary care practice are screened for falls and the quality of care for those who are at risk for falling has not improved in the past decade.

Accordingly, this project funded jointly by the National Institute on Aging and the Patient Centered Outcomes Research Institute (PCORI) is a multi-site cluster randomized clinical trial (RCT) of an evidence-based, multifactorial individually-tailored intervention to reduce the risk of serious fall injuries among non-institutionalized older persons.

2. AIMS

1. To conduct in partnership with patients and stakeholders a cluster randomized trial of the intervention in a sample of 6,000 participants from 80+ practices in 10 health care systems that reflect geographic and sociodemographic diversity. The trial will include features of an adaptive design, to facilitate “learning”, including a pre-specified, mid-term analysis.
2. To identify and evaluate jointly with patients and stakeholders the obstacles and facilitators of the post-trial scalability, sustainability, and dissemination of the fall injury prevention strategy.

3. STUDY DESIGN

STRIDE is designed as a cluster randomized, parallel group superiority trial with practices stratified by healthcare system and patients nested within practices. The unit of randomization is the practice to avoid the potential for contamination of controls, which could occur more easily if randomization was at the level of the participant or physician. The primary outcome is time to first serious fall injury assessed at the patient level. The original target sample size was 6000 participants from a target of 86 practices to detect a 20% reduction in serious fall injuries in the intervention group versus control group with 90% power. The target sample size was revised to 5,322 in December 13, 2017; recruitment ended after 20 months on March 31, 2017, with a total of 5,451 participants enrolled.

STRIDE SAP

STRIDE was designed with the following adaptive features:

1. Monitoring the accrual rate to determine whether the eligibility criteria should be altered if enrollment is lower than expected (e.g., by lowering the age entry criterion);
2. Monitoring the potential for ascertainment bias because of interactions between the FCMs and study participants and changing the primary outcome definition, if necessary;
3. Monitoring the primary outcome rate to determine whether the outcome needs to be adapted, e.g., from first serious fall injury to all serious fall injuries if the former rate is too low, affecting the power of the study;
4. Interim monitoring for efficacy and futility, if necessary; and
5. Refining the analytic methods based on the validity of the assumptions; such an adaptation will be done blinded to treatment, e.g., if the death rate is low, competing risks could be considered as a secondary, rather than a primary, analysis.

4. OUTCOMES

The primary and secondary outcome measures are summarized in Table 1.

Domain	Measure (1° & 2°)	Source, Frequency, and Sample
Fall-related	Serious fall injuries (1°)	Telephone interview every 4 months, supplemented by administrative claims/encounter data (including data from clinical trial sites and Medicare) for date and type of injury; medical record adjudication for discrepancies with fall-injury claims
	All fall injuries (2°)	Telephone interview every 4 months: serious fall injuries plus other injuries that may not come to medical attention
	Original operationalized definition of primary outcome (2°)	Telephone interview every 4 months, supplemented by administrative claims/encounter data (including data from clinical trial sites and Medicare) for date and type of injury
	All falls (2°)	Telephone interview every 4 months
Well-being	Concern about falling (2°)	Modified FES at baseline, 12 m and 24 m (telephone) in 720 participants, representing a random sample of participants enrolled in first 12 months
	Physical function and Disability (2°)	LL-FDI via CAT at baseline, 12 m and 24 m (telephone) in 720 participants
	Anxiety/Depressive symptoms (2°)	PROMIS scales measured at baseline, 12 m and 24 m (telephone) in 720 participants
CAT: Computer Adaptive Testing; FES: Fall Efficacy Scale; LL-FDI: Late-Life Function and Disability Instrument; PROMIS: Patient Reported Outcomes Measurement Information System		

STRIDE SAP

4.1 Primary Outcome

The primary outcome is serious fall injuries leading to medical attention, including non-vertebral fractures, joint dislocation, head injury, lacerations, and other major sequelae (e.g., rhabdomyolysis, internal injuries, hypothermia). A fall is defined using the traditional definition of a person unintentionally coming to rest on the ground or other lower level not as a result of a major intrinsic event (e.g. myocardial infarction or stroke) or an overwhelming external hazard (e.g. hit by a vehicle). The following will not be included as falls: a controlled or intentional movement to a chair or bed; a "near fall" in which the participant caught himself or herself before hitting the floor, ground, or object; and being knocked down by a substantial external force, like a moving vehicle. Fall injuries from height > 3 feet will not be included.

The definition of the primary outcome was modified on 6/1/2018 to reflect the recommendations of the Ad Hoc Expert Panel established by the NIA and NIA's concurrence with this recommendation. The definition of a serious fall injury was adapted to:

A fall resulting in:

(1) fracture other than thoracic/lumbar vertebral; joint dislocation; or cut requiring closure AND any medical attention;

OR

(2) head injury; sprain or strain; bruising or swelling; or other requiring hospitalization.

The original definition only required medical attention for a head injury; sprain or strain; bruising or swelling; or other – not a hospitalization.

4.2 Secondary Outcomes

The secondary outcomes include all fall injuries and all falls (regardless of injury), as well as indicators of well-being. All fall injuries include serious fall injuries as well as less severe falls that result in bruises, cuts, persistent pain, and restricted activities, but not necessarily medical attention. The four indicators of well-being are: fall efficacy, physical function/disability, anxiety, and depressive symptoms administered by brief instruments over the phone. The indicators of well-being will be measured at 12 and 24 months in a random subsample of 720 participants. The random subsample will be selected from year 1 enrollees to permit 24 month assessments within the trial duration of 3 years.

4.3 Tertiary Outcomes

The tertiary outcomes include hospitalizations and long-term nursing home admissions.

5. RANDOMIZATION

5.1 Method of Randomization

All participating clinical practices that met trial eligibility criteria were randomized at one time using covariate-constrained randomization with stratification by clinical site (healthcare system) to control for potential site differences. Covariate-constrained randomization was used to balance practice characteristics within and across the clinical sites (strata). The balancing

STRIDE SAP

covariates were practice size, geography (urban vs. rural), and race/ethnicity (primary identification nonwhite vs. white).

A published SAS macro was used to conduct the covariate-constrained randomization (Chaudhary and Moulton, 2006; Greene, 2017). The macro generates a set of randomizations that satisfy balance on practice size, geography and race/ethnicity both within and across strata. From this set of valid assignments, one was selected at random. Only the trial biostatisticians participated in the generation of the randomization. No one else from the trial was involved in the process. To minimize the risk of selection bias, practice site names were masked during the process. The practice site randomization assignments to treatment groups were released to the clinical sites only after careful vetting of the entire randomization process by the trial biostatisticians.

Practices will not be added after trial initiation. All available practices that met our eligibility criteria have been carefully vetted and have committed to the trial. The criteria included: sufficient number of age eligible patients (≥ 400), access to community resources (specifically, exercise programs), access to electronic health records (EHR) and availability of practice characteristics. Thus, additional practices are not readily available. The participating practices have more than enough age eligible patients ($> 80,000$) to meet the original target recruitment goal of 6,000 patients, assuming a conservative 10% enrollment rate, which is reasonable based on the pilot study data. If a randomized practice drops out of the trial, we expect to ascertain study outcomes in individual participants since follow-up is being conducted centrally.

5.3 Allocation Concealment

An important consideration, particularly in cluster trials, is allocation concealment to control for selection bias. Potential approaches include 1) randomizing after enrollment, 2) blinding the recruiters, 3) standardizing the enrollment process with adequate training of screeners and recruiters, and 4) covariate adjustment in the analysis. Because enrollment must occur after practices have been randomized in STRIDE, the first approach is not feasible. However, the possible effects of selection bias will be mitigated through approaches 2 and 3, along with covariate adjustment in the analysis, if necessary.

6. SAMPLE SIZE

6.1 Preliminary Data

Sample Size estimates were informed by preliminary data from MOBILIZE Boston, a longitudinal study of 765 community-living seniors, with monthly ascertainment of serious fall injuries. Although based solely on self-report, the operational definition of serious fall injury was otherwise the same as in the proposed trial. Analyses were restricted to 135 participants meeting STRIDE entry criteria, with a median follow-up of 2.8 years. The annual rate of first serious fall injury was 18% (95%CI: 14%-24%); a preliminary estimate of the overall serious fall injury rate (including recurrent events) was comparable, at 21% (95%CI: 16%-24%). For the proposed trial, we project an annual outcome rate in the control group of 14% to 18%, since fall injuries will be assessed every three months rather than monthly, and our protocol requires that serious fall injuries be confirmed by data from claims or medical records.

STRIDE SAP

Data from the Lifestyle Interventions and Independence for Elders (LIFE) Study and Assessing Care of Vulnerable Elders Practice Redesign for Improved Medical Care for Elders (ACOVEprime) were also examined in order to inform the outcome rate, but LIFE had a lower risk population and ACOVEprime primarily used Medicare claims data to ascertain fall rates. Data from MOBILIZE Boston and LIFE were used to help inform the loss and death rates. The annual loss rate in the absence of serious fall injury was 4% in MOBILIZE Boston, but this study did not have access to claims or EHR data. The rate in LIFE was less than 2% in 728 patients aged 75 years and older. The annual death rates in the absence of serious fall injury were less than 2% for both MOBILIZE Boston and the LIFE Study. Because the MOBILIZE Boston rate was based on only a few number of deaths and the LIFE Study enrolled a lower risk population because the intervention included an exercise component, we assumed a higher death rate for STRIDE.

6.2 Sample Size Determination for the Primary Outcome

Sample size was determined for a clustered design for time to first serious fall injury (the primary outcome) based on the logrank statistic in the presence of competing risk due to death. Table 2 presents sample size estimated using PASS version 12 (Kaysville, Utah) under the following assumptions:

1. type I error = 5% (2-sided) and 90% power;
2. a trial duration of 3 years with accrual periods of 1, 1.5 and 2 years (assuming uniform accrual);
3. equal allocation to intervention and control groups;
4. no adjustment for non-adherence to intervention (accounted for with conservative treatment effect);
5. all patients followed to end of the trial (max = 3 years);
6. a 20% reduction in serious fall injuries with intervention relative to control, assuming constant and proportional hazards. [This reduction, which would have considerable clinical and public health impact, is intermediate between that found in Yale FICSIT (31% reduction in all falls) and Connecticut Collaborative Falls Program (CCFP) (9% reduction in serious fall injuries), two prior multifactorial fall prevention studies. Because many aspects of our intervention will be implemented at the level of the patient (as in FICSIT) rather than geographic region (as in CCFP), our effect size should be closer to that of FICSIT than CCFP, making the sample size estimates given here conservative.]
7. 7% annual death rate without experiencing a serious fall injury (i.e., competing risk);
8. 3% annual loss to follow-up rate in the absence of serious fall injury or death (expected to be low due to the use of multiple sources, including claims and medical records data);
9. 3% inflation for the proposed interim monitoring for efficacy and futility; and
10. 53% inflation for the design effect of clustering, assuming an average of 70 participants enrolled per practice from 86 practices and an ICC of 0.0076 estimated from an analysis of serious fall injuries in the LIFE Study.

Based on Table 2, a target sample size of 6000 participants was selected to be accrued from 86 practices, each enrolling an average of 70 participants over a 1.5-year recruitment period. This sample size provided 90% power to detect a 20% reduction in the hazard rate with intervention

STRIDE SAP

relative to control for an annual first serious fall injury rate of 0.14 in the control group. The target number of serious fall injuries to detect this reduction is 845 events.

On December 13, 2017, a protocol amendment was approved extending the duration of the study from 36 months (18 months of recruitment and a minimum 18 months of follow-up) to 40 months (20 months of recruitment and a minimum of 20 months of follow-up). The target sample size was adjusted to 5,322 participants for a 40-month study instead of 6000 participants for a 36-month study. Recruitment ended after 20 months on March 31, 2017, with a total of 5,451 participants enrolled.

Table 2. Sample Size Estimates

Accrual Period (Years)	Annual Event Rate in the Control Group	Total Sample Size
1	0.14	5532
	0.16	4906
	0.18	4418
1.5	0.14	6030
	0.16	5332
	0.18	4792
2	0.14	6666
	0.16	5888
	0.18	5284

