Assessment of Ascertainment Bias. We will focus on patient-reported type 2 injuries (head injury; sprain or strain; bruising or swelling; or other) without an accompanying type 1 injury. We define Type 2a injuries as those requiring a hospitalization, Type 2b as those that do not require a hospitalization for which other medical attention was sought and Type 2c as those in which no medical attention was sought. Patient-reported events are used for the assessment of ascertainment bias because Type 2c events are not adjudicated. The proportion (p) of Type 2b events in intervention and control groups will be calculated. The denominator for the proportion can be all Type 2 events ($2a + 2b + 2c$) or only Type 2b and 2c. The difference in proportions with 90% confidence intervals will be calculated and reported. We propose a higher type I error rate for calculation of confidence intervals to provide for greater control of type 2 error because the cost of a missed bias could adversely affect study power even when differences are small. The strategy for assessing the latter is outlined below. Although it is possible that the intervention might "turn a Type 1 event into a Type 2 event," this effect should be negligible relative to the potential ascertainment bias.

Potential Effect of Ascertainment Bias on the Study Power. Using the proportions for intervention (p_i) and control (p_c), we will estimate the "excess" (i.e., due to ascertainment bias) number of Type 2 events in the intervention arm by comparing the observed vs. expected number of Type 2b events. The projected number of excess type 2b events in the intervention arm can be approximated by

(Observed number of Type 2b events in control) x (hypothesized ratio of events: intervention relative to control) x $(p_i/p_c - 1)$.

STRIDE SAP

The derivation is given in Appendix A. The projected excess number of events in the intervention arm will be used to assess its impact on the power of the trial using the observed control event rate and the hypothesized intervention effect. Note, the target number of primary outcomes to detect a hazard ratio of 0.80 with 90% power is 844: 382 intervention vs. 462 control, or a ratio of 0.827. Thus, an excess of 11 events in the intervention arm from 382 to 393, decreases the power to 80% for an annual control event rate of 0.14.

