Cluster randomized trials require an inflation to sample size (target number of events) to account for the correlation among patients within a cluster. The target number of events in STRIDE was first calculated for an unclustered design and then inflated for interim monitoring and the cluster design effect, which is a function of the intracluster correlation coefficient (ICC) and number enrolled per practice. The number of events for an unclustered design with a hazard ratio (HR) = 0.80 and 90% power is 844. This number was inflated by 1.03 for interim monitoring and 1.52 for the cluster design effect, giving a target number of first primary events of $1321 = 844 \times 1.52 \times 1.03$. The cluster design effect was estimated based on an ICC of 0.0076 from the LIFE trial, assuming clinical practices as clusters, and constant number enrolled/practice of 70 as $1 + (70-1)(0.0076)$. The design effect needs to be re-estimated for STRIDE because there was wide variability in the number enrolled per practice, and the ICC was estimated from LIFE, which randomized participants and not sites. Because there is no closed form estimate of the ICC for the complexity of the STRIDE trial design (i.e., a clustered survival trial with a competing risk of death), we will estimate the design effect using a variance inflation factor (VIF) method (i.e., variance for the intervention effect for the clustered model relative to the unclustered model), and then use the VIF

STRIDE SAP

to determine the target number of primary events as $844 \times 1.03 \times \text{VIF}$. The target number of primary events will then be used to determine information fraction for timing of the interim look. The VIF will be determined by the unblinded trial statisticians as it will involve modeling the intervention effect. The DSMB will be blinded to the actual intervention effect until the scheduled interim look.

2b. Monitoring the Accrual of Adjudicated Primary Outcomes in the Control Group

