The primary outcome is first adjudicated SFI. Because adjudication of outcomes will lag behind the accrual of patient reported SFI, an estimate of the conversion rate (with 95% confidence intervals) will be calculated from the accumulated data, i.e., proportion of reported events in which adjudication has been completed (i.e., resolved) that meet the definition of a primary study outcome. Separate conversion rates may need to be estimated for the different types of SFI (Types 1 and 2). The conversion rate will be used to estimate the projected number of adjudicated first SFI at the end of the 40-month trial based on the observed patient reported first SFI rate and the projected total person years of follow-up (PYF) accounting for censoring due to deaths and losses. The observed patient reported first SFI event rate will be estimated as the number of observed patient-reported first SFI divided by the observed total PYF. The projected adjudicated events will then be estimated as:

Projected adjudicated SFI = observed first patient reported SFI rate x projected total PYF x adjudication conversion rate.

A comparison of the projected number of adjudicated events with the target number of control events (723), after accounting for the estimated ICC, for 90% power (or, if necessary, 540 events for 80% power) will be used to assess whether an extension of follow-up is needed and for how long a duration (see 2c below).

As a supportive strategy, we will also calculate the control event rate. A control event rate of 0.14/year was assumed in the sample size calculations for 90% power; a rate of approximately 0.10/year is needed for 80% power. The sample size calculations also assumed a 7% annual death rate (competing risk) and 3% annual loss to follow-up (censoring) rate. We propose a cumulative incidence rate calculation (with 95% confidence intervals) that considers the censoring and competing risk rate, instead of the Kaplan Meier rate which counts losses and deaths as independent censoring. If the lower bound for the observed rate is greater than the hypothesized control rate of 0.14 for 90% power or 0.10 for 80%, then there is some assurance that the study is on target for 80%/90% power to detect the hypothesized effect, a hazard ratio of 0.80.

2c. Extending Follow-up or Adapting the Primary Outcome from First SFI to All SFI to Maintain Study Power

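### Section 6.2 gives 845 as the event target for a clustered design with 90% power, but 845 is the unclustered, uninflated count; Appendix B puts the design-stage target at 1,321.

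*SAP*

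**What the plan says.** Section 6.2 of the SAP states that the calculation is for a clustered design. Its assumptions include 3% inflation for interim monitoring and "53% inflation for the design effect of clustering", based on 70 participants per practice and an ICC of 0.0076. It selects 6,000 participants and says: "This sample size provided 90% power to detect a 20% reduction in the hazard rate with intervention". The control rate assumed there is 0.14 per year. The next sentence is: "The target number of serious fall injuries to detect this reduction is 845 events". It carries no qualifier and no cross-reference.

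Appendix B, Stage 2a, describes the same calculation differently: "The number of events for an unclustered design with a hazard ratio (HR) = 0.80 and 90% power is 844". It then adds both inflations: "This number was inflated by 1.03 for interim monitoring and 1.52 for the cluster design effect, giving a target number of first primary events". The product stated there is 1,321. Stage 2a treats this as a planning value: "The design effect needs to be re-estimated for STRIDE because there was wide variability in the number enrolled per practice". The update is to be 844 x 1.03 x VIF, where VIF is the observed variance inflation factor. Stage 2b then compares projected events with a "target number of control events (723), after accounting for the estimated ICC, for 90% power".

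Appendix B is not uniform, however. Stage 1 says "the target number of primary outcomes to detect a hazard ratio of 0.80 with 90% power is 844: 382 intervention vs. 462 control" without naming the scale, and the derivation of excess Type 2 events at the end of the monitoring plan repeats the 382 and 462 in the same way.

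**The concern.** The SAP calls two different numbers, 845 and 1,321, the target for the same outcome, effect size and power. Only 1,321 fits the clustered design that section 6.2 says it is sizing. In section 6.2 the 845 directly follows the 90% power statement and refers back to the reduction named there, so a reader will take the two together.

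This is the only event count in the main sample size section. Someone judging the accrued information from section 6.2 alone could conclude that 845 first events secure 90% power, when that number is well short of the plan's own target.

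**Working it through.** **Inputs from section 6.2.** Two-sided 5% type I error, 90% power, 1:1 allocation, hazard ratio 0.80; control rate 0.14 per year; death 7% and loss 3% per year; uniform accrual over 1.5 years in a 3-year trial; interim inflation 1.03; clustering inflation 1.53. **From Appendix B, Stages 1, 2a and 2b.** 844 events unclustered (382 and 462), design effect 1.52, target 1,321, control targets 723 (90% power) and 540 (80% power).

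**Step 1: reproduce 845.** Schoenfeld's formula gives

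4 x (1.960 + 1.2816)² / (ln 0.80)² = 844.1,

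which rounds up to 845; Appendix B gives 844. The formula contains no design effect and no interim inflation.

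**Step 2: reproduce 1,321.** The design effect is 1 + 69 x 0.0076 = 1.524.

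- With Appendix B's factor: 844 x 1.52 x 1.03 = 1,321.4.
- With section 6.2's factor: 844 x 1.53 x 1.03 = 1,330.1.

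The 1.52 and the 53% both approximate 1.524, and the gap between them is about 0.7%. That is not a separate defect. The ratio 845 / 1,321 is 0.64.

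**Step 3: check the scale of the Stage 2b figures.** For 90% power, 462 x 1.52 x 1.03 = 723.3, the stated 723. For 80% power the unclustered count is 4 x (1.960 + 0.8416)² / (ln 0.80)² = 630.5. Then 630.5 x 1.52 x 1.03 x 462/844 = 540, as stated. Both monitoring figures are on the inflated scale.

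**Step 4: events expected from 6,000 participants.** Treat the annual rates as constant hazards. Let h be the event hazard, s the sum of the event, death and loss hazards, A = 1.5 and T = 3. The probability of an observed first event is

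P = (h/s) x {1 − [exp(−s(T − A)) − exp(−sT)] / (sA)}.

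| Arm | h | s | P | Events per 3,000 |
|---|---|---|---|---|
| Control | 0.140 | 0.240 | 0.2416 | 724.7 |
| Intervention | 0.112 | 0.212 | 0.1990 | 597.1 |

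The total is 1,321.8 events. The mean probability is 0.2203, so 845 events would need only 845 / 0.2203 = about 3,836 participants.

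Table 2's rows for a control rate of 0.14 give the same picture: 5,532, 6,030 and 6,666 participants yield about 1,325, 1,328 and 1,329 events.

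**Step 5: power at 845 events under the planning design effect.** Power = Φ(0.2231 x √(E/4) − 1.96), where E is the effective number of events.

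| Adjustment | E | Power |
|---|---|---|
| 845 / 1.52 | 555.9 | 74.9% |
| 845 / 1.53 | 552.3 | 74.6% |
| 845 / (1.52 x 1.03) | 539.7 | 73.6% |
| 845 / (1.53 x 1.03) | 536.2 | 73.4% |

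**Step 6: the updating formula.** At VIF = 1, 844 x 1.03 x VIF is 869.3. It equals 845 only at VIF = 0.972, that is, only if clustering reduced the variance.

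**The case against.** The number 845 is not miscalculated. It is the correct logrank count for an individually randomised trial, and what is missing is a label. Stage 2a explains the scale fully, and section 7.1 sends the reader to Appendix B. Assumptions 9 and 10 can be read as inputs to the participant numbers in Table 2 rather than to the event count. No rule uses 845: the information fraction is set from 844 x 1.03 x VIF, and the trial ends by calendar time. The 73% to 75% power therefore describes a trial that nobody planned. The VIF argument also depends on keeping the 1.03, although the interim look later became optional; without it, 844 x VIF reaches 845 at a VIF of about 1.001. Finally, placing 1,321 beside the 53% in section 6.2 introduces a small mismatch with 1,330.

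Much of this stands, and it limits the weight of the point. Planned power is not short and no decision goes wrong. It does not remove the error. Section 6.2 presents 845 as the target for a clustered design, does not refer to Stage 2a, and is contradicted there. The unlabelled 844 in Stage 1 makes the appendix a less reliable guide. The VIF argument is about the formula as the SAP writes it, with the 1.03. Even without that factor, 845 would require essentially no clustering effect. The gap between 1,321 and 1,330 is rounding and can be covered by a few words.

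**Conclusion.** The point holds, as a minor error. The target stated in section 6.2 is on the wrong scale for the design and power beside it: 845 against a design-stage target of about 1,321, or 64%. The sample size of 6,000 already carries both inflations and agrees with 1,321, so there is no shortfall in planned power.

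The 1,321 is itself a planning value that rests on an ICC of 0.0076 and 70 participants per practice, and the SAP meant to replace the design effect with the observed VIF. The event yield of about 1,322 treats the annual rates as hazards. Read as annual probabilities, they give about 1,405 events, still far above 845.

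**What to change.** In section 6.2, replace the sentence on the event target with: *For an unclustered design without interim inflation, 844 first serious fall injuries are needed. With inflation for interim monitoring and clustering, the design-stage target is about 1,321 first events (about 723 in the control group), updated as 844 x 1.03 x VIF; see Appendix B, Stage 2a.*

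Leave the 53% and Table 2 as they are. The 1.5-year and 2-year rows at a rate of 0.14 (6,030 and 6,666) fit 1.53 better (6,038 and 6,670) than 1.52 (5,999 and 6,626). A few words saying that 53% and 1.52 both approximate 1.524 would spare a reader the 1,321 against 1,330 question.

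Leave the dated text of Appendix B unchanged, but add an editorial note at Stage 1 that 844 (382 and 462) and the 11-event illustration are on the unclustered scale. The same note at the derivation of excess Type 2 events is for consistency only, because the two counts enter there only through their ratio, 0.827, which a common multiplier does not change.

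The cost is SAP wording alone. The design effect, Table 2, sample size, monitoring rules and analysis do not change.
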